9.4.3 Electrocardiogram

For treatment-emergent ECG measurements, a summary of raw values and change from baseline values will be provided at each scheduled time point for the following standard 12-lead ECG measurements: RR (msec), HR (beats per minute [bpm]), PR (msec), QRS duration (msec), QT (msec), and QT corrected for HR intervals (QTcF [msec]). A corresponding listing will also be provided.

The number and percentage of subjects with at least 1 ECG event that meets the threshold criteria during the TE period will be summarized by time point. A corresponding listing will also be presented. This listing will include both scheduled and unscheduled visits. The threshold value criteria are provided in [Appendix G](#).

9.4.4 Vital Signs

For treatment-emergent vital signs measurements, the raw values and change from baseline values will be summarized at each scheduled time point for the following measurements: systolic and diastolic blood pressure (mm Hg), body temperature ($^{\circ}$ C), HR (bpm), and respiration rate (breaths per minute). A corresponding listing will also be provided.

The number and percentage of subjects with vital sign parameters that meet the threshold criteria during the TE period will be summarized for each scheduled time point. The threshold value criteria are provided in [Appendix G](#).

9.4.5 Pulse Oximetry

For treatment-emergent percent of oxygen saturation by pulse oximetry, a summary of raw values and change from baseline values will be provided at each scheduled time point.

9.4.6 Physical Examination

Physical examination findings will be presented as a subject data listing only.

9.4.7 Ophthalmologic Examination

Ophthalmologic examination findings will be presented as a data listing.

9.4.8 Other Safety Analysis

9.4.8.1 Serial Lung Function (Post-dose Spirometry)

For the 2-hour and 4-hour post-dose spirometry measurements on Day 1 and Week 2, a summary of raw values and the absolute change from the predose value for ppFEV₁ will be provided at each time point.

The number and percentage of subjects with ppFEV₁ decline ≥ 10 , ≥ 15 , and ≥ 20 percentage points in the absolute change from baseline in predose value will be summarized for scheduled visits.

In addition, the number and percentage of subjects with ≥ 0.10 L or ≥ 0.20 L decrease in the absolute change from baseline through Week 8 for FEV₁ will also be summarized for scheduled visit.

Subjects with ≥ 10 percentage points decrease in absolute change from baseline through Week 8 for ppFEV₁ or ≥ 0.10 L decrease in the absolute change from baseline through Week 8 for FEV₁ will be listed.

10 INTERIM AND DMC ANALYSIS

10.1 Interim Analysis

No formal interim analysis is planned.

10.2 DMC Analysis

An independent data monitoring committee (IDMC) was formed before study initiation to review the safety of the study. The IDMC's objectives and operational details were defined in a separate document (IDMC Charter) which was finalized before the first subject was screened in the study. The IDMC conducted regular planned safety reviews of study data as outlined in the IDMC Charter and IDMC Analysis Plan.

12 LIST OF APPENDICES

▪ Appendix A: Analysis Visit Windows for Safety and Efficacy Assessments

Table 12-1 Visit Window Mapping Rules			
Assessments	Visit¹	Target Study Day	Visit Window (in study days)
Safety Assessment			

 • Standard 12-lead ECG • Vital signs • Pulse oximetry • Chemistry 	Day 1	1	≤1 Pre-dose
	Week 2	15	[1*, 22]
	Week 4	29	(22, 43]
	Week 8	57	(43, 71]
	Safety Follow-up Visit	N/A	Nominal

 • Hematology 	Day 1	1	≤1 Pre-dose
	Week 2	15	[1*, 36]
	Week 8	57	[37, 71]
	Safety Follow-up Visit	N/A	Nominal

 • Urinalysis • Lipid panel • Vitamin levels 	Day 1	1	≤1 Pre-dose
	Week 8	57	[1*, 71]
	Safety Follow-up Visit	N/A	Nominal

 • Coagulation 	Day 1	1	≤1 Pre-dose
	Week 8	57	[1*, 71]
	Safety Follow-up	N/A	Nominal
Efficacy Assessment			

 • Spirometry (pre-dose) • CFQ-R^a • Weight and height 	Day 1	1	≤1 Pre-dose
	Week 2	15	[1*, 22]
	Week 4	29	(22, 43]
	Week 8	57	(43, 71]
	Safety Follow-up Visit	N/A	>71

 • LCI 	Day 1	1	≤1 Pre-dose
	Week 2	15	[1*, 22]
	Week 4	29	(22, 43]
	Week 8	57	(43, 71]

 • Sweat chloride 	Day 1	1	≤1 Pre-dose
	Week 8	57	[1*, 71]
	Safety Follow-up Visit	N/A	>71

* Only include day 1 post-dose measurements.

^a a CFQ-R is only required at the Safety Follow-up Visit for subjects who prematurely discontinue study treatment and do not have the ETT visit.

^b Physical examination at Day 1, Week 8 and Safety Follow-up Visit are abbreviated ones.

Note:

1. Visit name for analysis purpose is used to report data in tables and figures.
2. The analysis visit windows will be applied for both scheduled and unscheduled visits.
3. If no measurement is available within a visit window, the assessment will be considered missing for the visit.
4. If there is more than one measurement available within the same visit window for efficacy parameters, the record at the scheduled visit will be used. Otherwise,
 - The record closest to the target day will be used.
 - If there are multiple records with the same distance to the target day, the latest record will be used.
 - Assessments at early treatment termination (ETT) visit will follow the windowing rules for regular visits up to Week 8.
 - Assessments at safety follow-up (SFU) visit will follow the windowing rules for regular visits if they fall within the upper boundary of the window for Week 8, or remain as SFU if they go beyond the upper boundary of the window for Week 8.
5. If there is more than one measurement available within the same visit window for safety parameters, then
 - The record closest to the target day will be used.
 - If there are multiple records within the same distance from the target day, the latest record will be used; or
 - SFU visit will not be windowed; instead, it will be used according to the nominal visit in relevant analyses.
6. Spirometry assessments, BMI, weight, and height will be used for [REDACTED] safety purpose. Their measurements will follow the visit windowing rules for efficacy parameters.
7. For post-dose spirometry, Day 1 and Week 2 will be nominal.

Special handling for ECG:

- On Day 1, the pre-dose measurements will be collected as triplets; the average of the triplicate will be used as pre-dose measurement on Day 1. Only pre-dose measurement with nominal visit names related to the triplets shall be used in this average.
- For other post-dose visits, the visit window in the above table will apply.

▪ **Appendix B: Standards for Safety and Efficacy Variable Display in TFLs**

Continuous Variables

The precision for continuous variables has been specified in the Vertex Standard Programming Rules document (Version 1.0, December 2015):

Categorical Variables: Percentages will be presented to 1 decimal place.

▪ **Appendix D: Imputation Rules for Missing Prior/Concomitant Medication Dates**

Imputation rules for missing or partial medication start/stop dates are defined below:

1. Missing or partial medication start date:
 - a. If only DAY is missing, use the first day of the month.
 - b. If DAY and Month are both missing, use the first day of the year.
 - c. If DAY, Month and Year are all missing, use a date before the first dose date (in practical, use January 01, 2000 to impute).
2. Missing or partial medication stop date:
 - a. If only DAY is missing, use the last day of the month.
 - b. If DAY and Month are both missing, use the last day of the year.
 - c. If DAY, Month and year are all missing, assign ‘continuing’ status to stop date (in practical, use December 31, 2050 to impute).

In summary, the prior, concomitant or post categorization of a medication is described below.

Table 12-2 Prior, Concomitant, and Post Categorization of a Medication

Medication Start Date	Medication Stop Date		
	< First Dose Date of Study Drug	≥ First Dose Date and ≤ End Date of TE Period	> End Date of TE Period
< First dose date of study drug	P	PC	PCA
≥ First dose date and ≤ End date of TE period	-	C	CA
> End date of TE period	-	-	A

A: Post; C: Concomitant; P: Prior

▪ **Appendix E: Imputation Rules for Missing AE dates**

Imputation rules for missing or partial AE start date are defined below:

If only Day of AE start date is missing:

- If the full (or partial) AE end date is NOT before the first dose date or AE end date is missing, then:
 - If the AE start year and month are the same as that for the first dose date, then impute the AE start day as the day of first dose date;
 - Otherwise, impute the AE start day as 1.
- Otherwise, impute the AE start day as 1.

Compare the imputed AE start date with TE period to determine whether the AE is pretreatment AE, TEAE or post-treatment AE.

If Day and Month of AE start date are missing:

- If the full (or partial) AE end date is NOT before the first dose date or AE end date is missing, then:
 - If the AE start year is the same as that for the first dose date, then impute the AE start month and day as the month and day of first dose date;
 - Otherwise, impute the AE start month as January and day as 1.
- Otherwise, impute the AE start month as January and day as 1.

Compare the imputed AE start date with TE period to determine whether the AE is pretreatment AE, TEAE or post-treatment AE.

If Year of AE start date is missing:

If the year of AE start is missing or AE start date is completely missing then query site with no imputation. Also compare the full (or partial) AE end date to the first dose date. If the AE end date is before the first dose date then the AE should be considered as a pretreatment AE. Otherwise, the AE will be considered as TEAE.

▪ Appendix F: Details of GLI Equation for Calculating ppFEV₁

Percent predicted values will be calculated for parameters of FEV₁, FVC, FEV₁/FVC, and FEF_{25%-75%} using the Quanjer GLI-2012 Regression Equations and Lookup Tables.

The regression equations and lookup tables required to implement the Quanjer GLI-2012 predicted values are available in:

Quanjer GLI-2012 Regression Equations and Lookup Tables. Philip H. Quanjer, Sanja Stanojevic, Tim J. Cole, Janet Stocks. Version 7 April 2013. Available at:

<http://www.ers-education.org/guidelines/global-lung-function-initiative/tools/quantjer-gli-2012-regression-equations-and-lookup-tables.aspx>

Accessed Sep 11, 2017.

The instructions and tools on how to implement the Quanjer GLI-2012 equations are:

Implementing GLI-2012 regression equations. Philip H. Quanjer, Sanja Stanojevic, Tim J. Cole, Janet Stocks. Version 19 July 2015. Available at:

<http://www.ers-education.org/guidelines/global-lung-function-initiative/spirometry-tools/it-engineers-and-manufacturers.aspx>

Accessed Sep 11, 2017.

GLI-2012 - SAS Macro. Sanja Stanojevic. Version 2, 7 April 2013. Available at:

<http://www.ers-education.org/guidelines/global-lung-function-initiative/tools/sas-macro.aspx>

Accessed Sep 11, 2017.

Data handling rule for spirometry is as follows:

- Input age and height with at least 2 decimal place
- For race, map CRF black or AA to black, all other races in CRF (except white) are mapped to 'other'; multiple checks for race in CRF are also mapped to 'other'; white is a reference race in the equations and assumes 0 values for all race coefficients in the GLI equations.

▪ **Appendix G: Criteria for Threshold Analysis**

Table 12-3 Threshold Analysis Criteria for Clinical Chemistry, Hematology and Coagulation		
Parameter	Threshold Criteria	Comments
LFT		
ALT	>ULN - ≤ 3 xULN >3 - ≤ 5 xULN >5 - ≤ 8 xULN >8 - ≤ 20.0 xULN >20.0 x ULN	Per FDA DILI Guidance Jul 2009 and CTCAE
AST	>ULN - ≤ 3 xULN >3 - ≤ 5 xULN >5 - ≤ 8 xULN >8 - ≤ 20.0 xULN >20.0 x ULN	FDA DILI Guidance and CTCAE
ALT or AST	(ALT>ULN and ALT ≤ 3 xULN) or (AST>ULN and AST ≤ 3 xULN) (ALT>3 xULN and ALT ≤ 5 xULN) or (AST>3xULN and AST ≤ 5 xULN) (ALT>5 xULN and ALT ≤ 8 xULN) or (AST>5xULN and AST ≤ 8 xULN) (ALT>8 xULN and ALT ≤ 20 xULN) or (AST>8xULN and AST ≤ 20 xULN) ALT>20 xULN or AST> 20 xULN	FDA DILI Guidance
Alkaline Phosphatase	>ULN - ≤ 1.5xULN >1.5 - ≤ 2.5 xULN >2.5 - ≤ 5.0 x ULN >5.0 - ≤ 20.0 x ULN >20.0 x ULN	FDA DILI Guidance and CTCAE
Total Bilirubin	>ULN - ≤ 1.5 x ULN >1.5 - ≤ 2 x ULN >2 - ≤ 3 x ULN >3 - ≤ 10 x ULN >10 x ULN	FDA DILI Guidance and CTCAE
Direct Bilirubin	>ULN - ≤ 1.5 x ULN >1.5 - ≤ 2 x ULN >2 - ≤ 3 x ULN >3 - ≤ 10 x ULN >10 x ULN	Same Criteria as Total Bilirubin No CTCAE Not in DILI Guidance
ALT and Total Bilirubin	ALT>3xULN and TBILI>2xULN	FDA DILI Guidance Jul 2009
AST and Total Bilirubin	AST>3xULN and TBILI>2xULN	FDA DILI Guidance Jul 2009
(ALT or AST) and Total Bilirubin	(ALT>3xULN or AST>3xULN) and TBILI>2xULN	FDA DILI Guidance Jul 2009
GGT	>ULN - ≤ 2.5 x ULN >2.5 - ≤ 5.0 x ULN >5.0 - ≤ 20.0 x ULN >20.0 x ULN	CTCAE grade 1-4

Non-LFT Chemistry		
CPK	>ULN - ≤ 2.5 x ULN >2.5 - ≤ 5 x ULN >5 - ≤ 10x ULN >10 x ULN	CTCAE grades 1-4
Creatinine	>ULN - ≤ 1.5 x ULN >1.5 - ≤ 3.0 x ULN >3.0 - ≤ 6.0 x ULN >6.0 x ULN	CTCAE grades 1-4
Blood Urea Nitrogen	>ULN - ≤ 1.5 x ULN >1.5 - ≤ 3.0 x ULN	Same criteria as creatinine
	>3.0 - ≤ 6.0 x ULN >6.0 x ULN	No CTCAE
Sodium	Hyponatremia <LLN - ≥130 mmol/L <130 - ≥120 mmol/L <120 mmol/L	CTCAE grade 1, 3, 4 (No CTCAE grade 2)
	Hypernatremia >ULN - ≤ 150 mmol/L >150 mmol/L - ≤155 mmol/L >155 mmol/L - ≤ 160 mmol/L >160 mmol/L	CTCAE grade 1-4
Potassium	Hypokalemia <LLN - ≥ 3.0 mmol/L <3.0 - ≥ 2.5 mmol/L <2.5 mmol/L	CTCAE grade 1&2, 3, 4 (Grade 1 and 2 are the same)
	Hyperkalemia >ULN - ≤ 5.5 mmol/L >5.5 - ≤ 6.0 mmol/L >6.0 - ≤ 7.0 mmol/L >7.0 mmol/L	CTCAE grade 1-4
Glucose	Hypoglycemia <3.0 - ≥ 2.2 mmol/L <2.2 - ≥ 1.7 mmol/L <1.7 mmol/L	CTCAE grade 1-4
	Hyperglycemia >ULN - ≤ 8.9 mmol/L >8.9 - ≤ 13.9 mmol/L >13.9 - ≤ 27.8 mmol/L >27.8 mmol/L	CTCAE grade 1-4
Albumin	<35 - ≥ 30 g/L <30 - ≥ 20 g/L <20 g/L	CTCAE grade 1-3
Amylase	>ULN - ≤ 1.5 x ULN >1.5 - ≤ 2.0 x ULN >2.0 - ≤ 5.0 x ULN >5.0 x ULN	CTCAE grade 1-4
Lipase	>ULN - ≤ 1.5 x ULN >1.5 - ≤ 2.0 x ULN >2.0 - ≤ 5.0 x ULN >5.0 x ULN	CTCAE grade 1-4

Calcium	Hypercalcemia >ULN - ≤ 2.9 mmol/L >2.9 - ≤ 3.1 mmol/L >3.1 - ≤ 3.4 mmol/L >3.4 mmol/L	CTCAE grade 1-4
	Hypocalcemia <LLN - ≥ 2.0 mmol/L <2.0 - ≥ 1.75 mmol/L <1.75 - ≥ 1.5 mmol/L <1.5 mmol/L	CTCAE grade 1-4
Magnesium	Hypermagnesemia >ULN - ≤ 1.23 mmol/L >1.23 - ≤ 3.30 mmol/L >3.30 mmol/L	CTCAE grade 1, 3, 4 No CTCAE grade 2
	Hypomagnesemia <LLN - ≥ 0.5 mmol/L <0.5 - ≥ 0.4 mmol/L <0.4 - ≥ 0.3 mmol/L <0.3 mmol/L	CTCAE grade 1-4
Inorganic phosphate	Hypophosphatemia <0.74 - ≥ 0.6 mmol/L <0.6 - ≥ 0.3 mmol/L <0.3 mmol/L	CTCAE grade 1-4
Lipid Panel		
Total Cholesterol	>ULN - ≤ 7.75 mmol/L >7.75 - ≤ 10.34 mmol/L >10.34 - ≤ 12.92 mmol/L >12.92 mmol/L	CTCAE grade 1-4
Triglycerides	>1.71 - ≤ 3.42 mmol/L >3.42 - ≤ 5.7 mmol/L >5.7 - ≤ 11.4 mmol/L >11.4 mmol/L	CTCAE grade 1-4
Hematology		
WBC	WBC decreased <LLN - ≥ 3.0 x 10 ⁹ /L <3.0 - ≥ 2.0 x 10 ⁹ /L <2.0 - ≥ 1.0 x 10 ⁹ /L <1.0 x 10 ⁹ /L	CTCAE grade 1-4
	Leukocytosis >100 x 10 ⁹ /L	CTCAE grade 3 (only Grade available)
Lymphocytes	Lymphocyte decreased <LLN - ≥ 0.8 x10 ⁹ /L <0.8 - ≥ 0.5 x10 ⁹ /L <0.5 - ≥ 0.2 x10 ⁹ /L <0.2 x10 ⁹ /L	CTCAE grade 1-4
	Lymphocyte increased >4 - ≤ 20 x10 ⁹ /L >20 x10 ⁹ /L	CTCAE grade 2, 3 (only Grades available)

Neutrophils	Neutrophil decreased $<LLN - \geq 1.5 \times 10^9 /L$ $<1.5 - \geq 1.0 \times 10^9 /L$ $<1.0 - \geq 0.5 \times 10^9 /L$ $<0.5 \times 10^9 /L$	CTCAE grade 1-4
Hemoglobin	Hgb decreased (anemia) $<LLN - \geq 100 \text{ g/L}$ $<100 - \geq 80 \text{ g/L}$ $< 80 \text{ g/L}$	CTCAE grade 1-3
	Hgb increased $>ULN - \leq 20 \text{ g/L above ULN}$ $>20 \text{ g/L above ULN} - \leq 40 \text{ g/L above ULN}$ $>40 \text{ g/L above ULN}$	CTCAE grade 1-3
Platelets	Platelet decreased $<LLN - \geq 75.0 \times 10^9 /L$ $<75.0 - \geq 50.0 \times 10^9 /L$ $<50.0 - \geq 25.0 \times 10^9 /L$ $<25.0 \times 10^9 /L$	CTCAE grade 1-4
Coagulation		
Activated partial thromboplastin time (PTT)	$>ULN - \leq 1.5 \times ULN$ $>1.5 - \leq 2.5 \times ULN$ $>2.5 \times ULN$	CTCAE grade 1-3
Prothrombin time (PT) International Normalized Ratio (INR)	$>ULN - \leq 1.5 \times ULN$ $>1.5 - \leq 2.5 \times ULN$ $>2.5 \times ULN$	CTCAE grade 1-3

Table 12-4 Threshold Criteria for ECGs

Ref.: CPMP 1997 guideline.

Parameter	Threshold	Comments
HR	Bradycardia	Per HV grade 2, 3, plus shift change
	$<50 \text{ bpm}$ $<45 \text{ bpm}$ Decrease from baseline $\geq 10 \text{ bpm}$ Decrease from baseline $\geq 20 \text{ bpm}$ $<50 \text{ bpm}$ and decrease from baseline $\geq 10 \text{ bpm}$ $<50 \text{ bpm}$ and decrease from baseline $\geq 20 \text{ bpm}$	
	Tachycardia	Per HV grade 1, 2, 3, plus shift change
	$>100 \text{ bpm}$ $>115 \text{ bpm}$ $>130 \text{ bpm}$ Increase from baseline $\geq 10 \text{ bpm}$ Increase from baseline $\geq 20 \text{ bpm}$ $>100 \text{ bpm}$ and increase from baseline $\geq 10 \text{ bpm}$ $>100 \text{ bpm}$ and increase from baseline $\geq 20 \text{ bpm}$	

PR	≥ 240 ms ≥ 300 ms ≥ 200 ms and increase from baseline ≥ 40 ms ≥ 200 ms and increase from baseline ≥ 100 ms
QRS	> 110 ms > 160 ms Increase from baseline ≥ 20 ms Increase from baseline ≥ 40 ms
QTc/QTcF	> 450 ms (Male) > 470 ms (Female) ≥ 500 ms Increase from baseline > 10 ms Increase from baseline > 20 ms Increase from baseline > 40 ms Increase from baseline > 60 ms

Table 12-5 Threshold Criteria for Vital Signs

Parameter	Threshold Criteria	Comments
HR	Same criteria as above in ECG category	
SBP	SBP increased > 140 mmHg > 160 mmHg > 10 mmHg increase from baseline > 20 mmHg increase from baseline > 140 mmHg & > 10 mmHg increase from baseline > 140 mmHg & > 20 mmHg increase from baseline > 160 mmHg & > 10 mmHg increase from baseline > 160 mmHg & > 20 mmHg increase from baseline	809/770 analyses
	SBP decrease < 90 mmHg < 80 mmHg > 10 mmHg decrease from baseline > 20 mmHg decrease from baseline < 90 mmHg and > 10 mmHg decrease from baseline < 90 mmHg and > 20 mmHg decrease from baseline < 80 mmHg and > 10 mmHg decrease from baseline < 80 mmHg and > 20 mmHg decrease from baseline	Per HV grade 1, 3, plus shift change

DBP	
DBP increased
 
>90 mmHg >100 mmHg >5 mmHg increase from baseline >10 mmHg increase from baseline
 
>90 mmHg and >5 mmHg increase from baseline >90 mmHg and >10 mmHg increase from baseline >100 mmHg and >5 mmHg increase from baseline >100 mmHg and >10 mmHg increase from baseline
 <hr/> 
DBP decreased
 
<60 mmHg <45 mmHg >5 mmHg decrease from baseline >10 mmHg decrease from baseline
 
<60 mmHg and >5 mmHg decrease from baseline <60 mmHg and >10 mmHg decrease from baseline <45 mmHg and >5 mmHg decrease from baseline <45 mmHg and >10 mmHg decrease from baseline
	809/770 analyses
Weight	
Weight gain
 
≥5 % increase from baseline ≥10 % increase from baseline ≥ 20% increase from baseline
 <hr/> 
Weight loss
 
≥5 % decrease from baseline ≥10 % decrease from baseline ≥ 20% decrease from baseline
	
CTCAE grade 1-3
 <hr/> 
CTCAE grade 1-3

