#### **11.5.6 Electrocardiograms**

Standard 12-lead ECGs will be performed using a machine with printout according to the Schedule of Assessments ([Table 3-1](#)). Additional standard 12-lead ECGs will be performed at any other time if clinically indicated. The performance of all ECGs will adhere to the following guidelines:

- The subject will be instructed to rest in the supine position for at least 5 minutes before having an ECG performed.
- The ECG will be performed before any other procedures that may affect heart rate, such as blood draws.

Clinically significant ECG abnormalities occurring during the study through the Safety Follow-up Visit will be recorded as AEs.

To ensure safety of the subjects, a qualified individual at the study site will make comparisons to baseline measurements. If the QTcF is increased by >45 msec from the baseline or an absolute QTcF value is  $\geq 500$  msec for any scheduled ECG, 2 additional ECGs will be performed approximately 2 to 4 minutes apart to confirm the original measurement. If either of the QTcF values from these repeated ECGs remains above the threshold value (>45 msec from baseline or  $\geq 500$  msec), a single ECG will be repeated at least hourly until QTcF values from 2 successive ECGs fall below the threshold value that triggered the repeat measurement. A subject with a QTcF value above the threshold value will discontinue dosing.

Further details pertaining to ECGs will be provided to sites in the ECG Manual.

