#### **12.3.4.3 Electrocardiogram**

For treatment-emergent ECG measurements, a summary of raw values and change from baseline values will be provided by treatment group and visit for the following standard 12-lead ECG measurements: RR (msec), HR (beats per minute [bpm]), PR (msec), QRS duration (msec), QRS axis (degrees), QT (msec), and QT corrected for HR intervals (QTcF [msec]).

The number and percentage of subjects with at least 1 ECG event outside of the threshold criteria during the TE period will be summarized overall and by treatment group. The threshold value criteria will be provided in the SAP.

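### When a prolonged QTcF is repeated on the same day, the SAP's visit-window rule puts the recovered value, not the scheduled one, into the by-visit ECG summaries

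*SAP*

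**What the plan says.** **Repeat rule (Protocol 11.5.6).** A scheduled ECG with QTcF more than 45 msec above baseline, or at least 500 msec, leads to two further ECGs a few minutes apart. If either is still above the threshold, "a single ECG will be repeated at least hourly until QTcF values from 2 successive ECGs fall below the threshold value" that set off the repeats.

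**Record selection (SAP Appendix A).**
- Windows are defined in study days, and Note 2 says: "The analysis visit windows will be applied for both scheduled and unscheduled visits".
- Note 5, for safety parameters with several records in a window: "The record closest to the target day will be used"; then "If there are multiple records within the same distance from the target day, the latest record will be used".
- Note 4, for efficacy parameters, starts differently: "the record at the scheduled visit will be used". Note 5 has no such preference.
- The special handling for ECGs averages the Day 1 pre-dose triplicate only. "For other post-dose visits, the visit window in the above table will apply".
- The Safety Follow-up Visit is not windowed for safety parameters; it is used as nominal.

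**ECG outputs (SAP 9.4.3).** There are three:
- values and changes from baseline at each scheduled time point;
- the number and percentage of subjects with at least one "ECG event that meets the threshold criteria during the TE period will be summarized by time point";
- a listing of threshold events that covers unscheduled visits.

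**Protocol count.** Protocol 12.3.4.3 has subjects with at least one threshold event "during the TE period will be summarized overall and by treatment group". SAP section 4 says the SAP prevails where its methods differ from the protocol's.

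**The concern.** A repeat ECG is taken because the scheduled value was high, and a confirmed sequence stops because the value has come down. A rule that keeps the last record of that sequence therefore selects on the outcome, and always in the same direction. The kept record may also be hours later than the scheduled pre-dose ECG that the table claims to show.

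At stake are the by-visit QTcF summaries. The subjects whose values are replaced include those with a confirmed elevation that meets the protocol's own criterion for stopping dosing. There is a second, conditional question: whether the threshold-event table uses the same windowed records. SAP 9.4.3 does not say.

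**Working it through.** The plan states no figure to reproduce; this is a check of a data-selection rule. The QTcF values below are assumed, because the documents give none.

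**Step 1: do the repeats tie?** Distance = |study day − target day|. At Week 4 (target day 29), every ECG taken on Day 29 has distance |29 − 29| = 0. The same holds for any single day, so time of day decides and the latest record is kept.

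**Step 2: what is the latest record?** In a confirmed sequence the last two values are below the trigger by the protocol's stopping rule. In an unconfirmed one, neither repeat is above it. Either way, the last record of a completed sequence no longer exceeds the trigger.

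**Step 3: apply Note 5 and compare with the maximum.** The rows are the QTcF categories in SAP Table 12-4, with the male absolute cut-off (>450 ms).

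| Case | Baseline | Same-day series | Kept by Note 5 | Rows met by kept record | Maximum | Rows met by maximum |
|---|---|---|---|---|---|---|
| 1 | 400 | 465, 462, 463, 450, 438, 436 | 436 (+36) | >10, >20 | 465 (+65) | >450, >10, >20, >40, >60 |
| 2 | 400 | 465, 462, 463, 455, 444, 442 | 442 (+42) | >10, >20, >40 | 465 (+65) | >450, >10, >20, >40, >60 |
| 3 | 440 | 505, 503, 502, 498, 497 | 497 (+57) | >450, >10, >20, >40 | 505 (+65) | >450, ≥500, >10, >20, >40, >60 |
| 4, not confirmed | 400 | 465, 430, 428 | 428 (+28) | >10, >20 | 465 (+65) | >450, >10, >20, >40, >60 |

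In case 3 the first value meets both triggers, and the series is stopped on the 500 msec one. If the 45 msec trigger must clear too, the ECGs continue until the value is no higher than 440 + 45 = 485. The kept record is then at most +45.

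**Step 4: by-visit summaries.** In case 1 the visit shows 436 instead of 465, a difference of 29 msec for that subject. With 40 + 12 = 52 planned TEZ/IVA subjects (Protocol Table 12-1), all with an ECG at that visit, the mean moves by 29/52 = 0.56 msec. The maximum is also among the planned summary statistics; this subject contributes +36 to it instead of +65.

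**Step 5: threshold-event table, two readings.**
- *All treatment-emergent records count.* No event is lost.
- *One windowed record per visit counts.* A recovered value of at least 500 msec always leaves the ≥500 row. A sequence that has cleared the 45 msec trigger cannot be in the >60 row. It leaves >40 only if it ends at +40 or less, as in case 1 but not case 2. One such subject among 52 is 1/52 = 1.9%, shown as 0% in the >60 row.

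**Step 6: which reading does the text favour?** For the first: the count is of subjects with at least one event over the whole treatment-emergent period, and SAP 9.1 feeds unscheduled values into on-treatment maxima and maximum changes for safety analyses. For the second: the layout is by time point; Note 1 makes the windowed visit the one reported in tables; unscheduled visits are mentioned for the listing but not for the table; and 9.4.3 defines no maximum-QTcF output to which the SAP 9.1 rule would apply. SAP 9.4.2, by contrast, counts laboratory events by treatment group and overall, with no time point. The text does not settle it.

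**The case against.** A reader might infer that the ECG tables drop the QTcF event altogether. The documents do not support that. The threshold count is worded as at least one event during the treatment-emergent period, and the SAP 9.1 rule on maxima points to using all records. The listing includes unscheduled ECGs. Clinically significant ECG abnormalities are recorded as adverse events. A confirmed elevation that stops dosing would probably reach the adverse event tables, which do not use visit windows, and discontinuation is tabulated in disposition. Lower threshold rows can still be met. Nor does the SAP abandon the treatment-group split: section 9.4 presents safety endpoints by treatment group and overall. What it lacks is an explicit across-visit count for ECGs.

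A reader might also extend the point to vital signs, which are likewise summarised by scheduled time point. The protocol has no repeat-until-normal rule for them, so the latest same-day value is not low by design.

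Two further objections have weight. Such events may be rare: Protocol 9.5 cites a thorough QT study that showed no prolongation. And preferring the scheduled ECG admits values that repeats do not confirm, as in case 4.

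None of this answers the point on the by-visit value and change summaries. For those, Note 5 applies as written, and no ECG exception removes its effect.

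**Conclusion.** The concern holds for the by-visit QTcF value and change summaries: when repeats fall on the same study day, they show the recovered value, which biases them towards no effect. For the threshold-event table it is conditional on reading the by-time-point layout as one windowed record per visit. The ambiguity is worth removing, because the SAP prevails over the protocol's clearer count.

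The size cannot be quantified, since no frequency of such sequences is given. The 0.56 msec and the 1.9% shown as 0% each assume one affected subject among 52 and invented QTcF values; the second also assumes the unfavourable reading.

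The conclusion assumes that the repeats are completed on one study day and that no other ECG in the window lies nearer the target day. Repeats that run past midnight have a different distance, so the tie no longer covers the whole sequence. The nominal Safety Follow-up ECG is outside the mechanism.

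**What to change.** 1. In SAP 9.4.3, count each subject once on the worst treatment-emergent value over all scheduled and unscheduled ECGs, overall and by treatment group, in line with Protocol 12.3.4.3. State that this count does not pass through the Note 5 selection. Keep the by-time-point table as a supplement.
2. In Appendix A Note 5, use the scheduled-visit record for by-visit ECG summaries when same-day repeats exist, as Note 4 does for efficacy.

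The cost is SAP wording and a small programming change, with no new data. The downside is that a scheduled value not confirmed by its repeats would enter the by-visit summary, and the ECG tables may look slightly less favourable.

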9.4.2 Clinical Laboratory

For treatment-emergent laboratory measurements, the raw values and change from baseline values of the continuous hematology, chemistry, vitamin, lipids and coagulation results will be summarized in SI units at each scheduled time point.

The number and percentage of subjects with events meeting threshold criteria laboratory event during the TE period will be summarized by treatment group and overall. The threshold analysis criterion shift from baseline will also be summarized for selected laboratory parameters. The threshold criteria are provided in [Appendix G](#).

Results of urinalysis and the urine/serum pregnancy test will be listed in individual subject data listings only.

In addition, a listing of each subject's liver function test (LFT), non-LFT chemistry, hematology, vitamin, lipid, and coagulation results outside the reference ranges will be provided. This listing will include data from scheduled and unscheduled visits.

For liver function tests (LFTs) (i.e. alanine aminotransferase [ALT], aspartate aminotransferase [AST], alkaline phosphatase [ALP], and total bilirubin), the following additional analyses will be presented:

- A listing of subjects with elevated LFT results during the TE period will be presented. For each subject in the listing, LFT assessments at all the time points will be included (scheduled and unscheduled).
- Mean values (\pm SD) will be plotted by visit, and box plots of the LFT values/ULN will be plotted by visit.

Summary tables for the shift from baseline to the value at Week 8 will be provided for vitamin levels and the lipid panel. Box plots of vitamin levels and the lipid panel will also be plotted against visit.

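### SAP Table 12-3 labels hypoglycemia and hypophosphatemia as CTCAE grades 1 to 4 but prints three bands each, which may leave mild low values out of the by-arm threshold counts

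*SAP*

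**What the plan says.** Table 12-3 in SAP Appendix G sets the laboratory cut-offs for the threshold analysis. Its comment column often names the CTCAE grades that the bands represent. Two rows matter here, both annotated as grades 1 to 4:

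- Glucose, low: "Hypoglycemia <3.0 - ≥ 2.2 mmol/L <2.2 - ≥ 1.7 mmol/L <1.7 mmol/L"
- Inorganic phosphate, low: "Hypophosphatemia <0.74 - ≥ 0.6 mmol/L <0.6 - ≥ 0.3 mmol/L <0.3 mmol/L"

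The calcium and magnesium rows carry the same annotation and have four bands, the first starting at LLN:

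- "Hypocalcemia <LLN - ≥ 2.0 mmol/L <2.0 - ≥ 1.75 mmol/L <1.75 - ≥ 1.5 mmol/L <1.5 mmol/L"
- "Hypomagnesemia <LLN - ≥ 0.5 mmol/L <0.5 - ≥ 0.4 mmol/L <0.4 - ≥ 0.3 mmol/L <0.3 mmol/L"

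SAP 9.4.2 uses these cut-offs to count subjects with threshold events during the treatment-emergent period, by treatment group and overall. It adds: "The threshold analysis criterion shift from baseline will also be summarized for selected laboratory parameters". Protocol 12.3.4.2 also plans the threshold summary with shifts and leaves the criteria to the SAP.

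**The concern.** Four grades cannot be mapped onto three bands. A programmer cannot tell from the table whether the first printed band is grade 1, grade 2 or both. Neither row has a band running from LLN down to its first fixed cut, so a mildly low glucose or phosphate may meet no criterion.

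What is at stake is the by-arm count of mild low values for two analytes. Mild lows in calcium, magnesium, sodium and potassium are counted from LLN, so one table would treat neighbouring electrolytes and metabolites differently without saying why. If either analyte is among those selected for the shift summary, the same gap carries over; the SAP does not name the selected parameters.

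**Working it through.** There is no sample-size or power figure to reproduce. The check has three steps: count bands against labels, look at how the table handles intended exceptions, and pass test values through the printed cut-offs.

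**1. Bands against labels.** 29 rows or sub-rows of Table 12-3 give specific CTCAE grade numbers.

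| Label | Rows | Rows where band count fits the label |
|---|---|---|
| Grades 1 to 4 | 19 | 17 |
| Grades 1 to 3 | 5 | 5 |
| Grades 1, 3, 4 | 2 | 2 |
| Grades 1 and 2 combined, 3, 4 | 1 | 1 |
| Grades 2, 3 | 1 | 1 |
| Grade 3 only | 1 | 1 |
| Total | 29 | 27 |

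The two misfits are hypoglycemia and hypophosphatemia, each with 3 bands under a 4-grade label. Eight rows labelled grades 1 to 4 concern low values. The other six (calcium, magnesium, white cells, lymphocytes, neutrophils, platelets) all start at LLN.

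**2. How intended three-band rows are marked.** Hyponatremia and hypermagnesemia list grades 1, 3 and 4 with the note "No CTCAE grade 2". Hypokalemia has the note "Grade 1 and 2 are the same", and its first band still starts at LLN. Albumin, "<35 - ≥ 30 g/L <30 - ≥ 20 g/L <20 g/L", starts at a fixed cut but is labelled grades 1 to 3, which fits its three bands. The glucose and phosphate rows have neither a note nor a fitting label.

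**3. Test values through the printed cut-offs.**

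| Analyte | In no band | In first band | In second band | In third band |
|---|---|---|---|---|
| Glucose (mmol/L) | 3.6, 3.3, 3.0 | 2.9 | 2.0 | 1.6 |
| Phosphate (mmol/L) | 1.0, 0.8, 0.74 | 0.73 | 0.5 | 0.2 |

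The uncounted low range is therefore from 3.0 mmol/L up to LLN for glucose, and from 0.74 mmol/L up to LLN for phosphate. Each range is empty if the laboratory's LLN is at or below that cut. The documents give no LLN for either analyte.

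**The case against.** **The intended correction is not proven.** A dropped band, two merged grades or a wrong label would each produce what is printed. This stands. The sibling rows make a dropped band the likeliest reading, but the documents alone do not settle it. Every one of these explanations still requires an edit.

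**A first cut that is not LLN is not an error in itself.** This also stands. Albumin starts at a fixed value. Triglycerides (above 1.71 mmol/L), lymphocyte increase (above 4 x 10^9/L) and leukocytosis (above 100 x 10^9/L) do too. A reader might infer that undercounting is confined to glucose and phosphate; the table does not support that, since other fixed first cuts can also leave out-of-range values uncounted. What is particular to these two rows is the conflict between label and bands.

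**Other outputs capture these values.** In large part they do. SAP 9.4.2 summarises continuous chemistry values and changes at each scheduled time point and lists non-LFT chemistry results outside the reference ranges. Protocol 11.5.2 makes clinically significant abnormal results adverse events, which are tabulated by arm. The secondary safety endpoint concerns clinically significant laboratory changes, so mild values judged not significant fall outside it. None of these outputs, however, gives a by-arm count of mild low values. A reader might infer that affected children would be reported as having no abnormality at all; the documents do not support that.

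**The size invites a guess.** Suppose random glucose is normal with mean 5.0 mmol/L, with three independent samples per child (Weeks 2, 4 and 8) in the 52 children (40 + 12) targeted for TEZ/IVA. The expected number of children with at least one value in the gap is 52 x [1 - (1 - p)^3], where p = P(below LLN) - P(below 3.0). With SD 0.7 and LLN 3.6, p = 2.28% - 0.21%, or about 2.06% before rounding, giving about 3 children. Varying SD over 0.6 to 0.8 and LLN over 3.3 to 3.9 gives 0.3 to 11, and an LLN of 3.0 or less gives none. Mean, SD, LLN and independence are all assumed, so this shows only that the documents do not fix the size.

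**A line may have been lost in reading the PDF.** This cannot be fully excluded. Both rows nevertheless read as complete, contiguous bands, and the LLN entries survive in neighbouring rows.

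**Conclusion.** The inconsistency is real and internal to the SAP: two of 19 rows labelled grades 1 to 4 have three bands, with no note to explain it. The reporting consequence is conditional. Only if the central laboratory's LLN exceeds 3.0 mmol/L (glucose) or 0.74 mmol/L (phosphate) are values below LLN but at or above the cut left out of the by-arm threshold counts.

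The impact is minor. SAP 9.4 makes all safety analysis descriptive and advises caution with the small control groups. The same cut-offs apply to every arm, and no efficacy conclusion depends on them. The number of children affected cannot be estimated from the documents. The point is still worth acting on, because it concerns a counting rule that can change reported numbers.

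**What to change.** Reconcile bands and label in both rows before the tables are programmed. The preferred change follows the calcium and magnesium rows and uses the central laboratory's own LLN:

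- Hypoglycemia: add a first band, below LLN to at least 3.0 mmol/L.
- Hypophosphatemia: add a first band, below LLN to at least 0.74 mmol/L.

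Both rows then have four bands and fit their label. If three bands are intended, correct the label or add a note on the merged or absent grade, as was done for sodium, potassium and hypermagnesemia.

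The cost is two cells in Table 12-3 and, with the preferred change, one extra output line per analyte. No new data are needed. The downside is that reported counts of mild low values may be slightly higher.
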